## 8.1 Stroke

The risk of stroke after treatment with the study device is low. However, if stroke occurs, the subject should be appropriately treated according to institutional standards. The investigator should obtain an NIH Stroke Scale within 7 days after stroke and record the value in the CRF.

 Cerus Endovascular	Document Number	Rev F	Page 17 of 34
	DNX065-01		
Design History Document	Title		
Confidential & Proprietary	Clinical Investigation Plan, Contour Neurovascular System™		

## 8.2 Independent Medical Monitor

An independent Medical Monitor will be appointed for the study who will be qualified by background and training and have expertise in neurovascular treatment of IAs. The independent Medical Monitor will review all adverse events to ensure they are reported accurately and in sufficient detail, and will make a final determination regarding relatedness to the investigational device and/or procedure. The Medical Monitor will not be an investigator on the study and will not be affiliated with a clinical site that is participating in the study.

## 8.3 Adverse Event Reporting/Analysis

In compliance with MEDDEV 2.7/3, 2015, for pre-market studies, the Sponsor is responsible for submitting reports to the Competent Authority as required by the applicable regulations and guidelines.

Specific requirements are as follows:

*Table 5 Sponsor Adverse Event Reporting*

Event	CA Reporting Timelines
SAE which indicates an imminent risk of death, serious injury, or serious illness and that requires prompt remedial action for other patients/subjects, users or other persons or a new finding to it	Immediately, but not later than 2 calendar days after awareness by Sponsor of a new reportable event or of new information in relation with an already reported event, per MEDDEV 2.7/3
Any SAE	Immediately, but not later than 7 calendar days following the date of awareness by Sponsor, per MEDDEV 2.7/3
Any investigational device deficiency that might have led to a SAE if a) suitable action had not been taken or b) intervention had not been made or c) if circumstances had been less fortunate	Same as above
New findings/updates in relation to already reported events	Same as above

The Investigative Site shall report all SAEs to the study sponsor or the sponsor's designee and independent Medical Monitor within 48 hours of occurrence.

## 9 Statistical Analysis

 Cerus Endovascular	Document Number	Rev F	Page 18 of 34
	DNX065-01		
Design History Document	Title		
Confidential & Proprietary	Clinical Investigation Plan, Contour Neurovascular System™		

## 9.1 General Principles

This is a pilot study intended to collect and report data on the use of the Contour Neurovascular System™.

The primary analysis for all baseline characteristics and study variables will include all available data for all enrolled subjects. Standard summary statistics will be calculated for all study variables. For continuous variables, statistics will include means, standard deviations, medians and ranges. Categorical variables will be summarized in frequency distributions.

Statistical analyses will be conducted in SAS version 9.3 or above (SAS Institute, Cary, N.C.), R version 3.2 or above (R Core Team, <http://www.R-project.org>) or another validated statistical software package.

For adverse event reporting, the primary analysis will be based on subject counts, not event counts. Both subject counts and event counts will be presented in tabular summaries of results.

As this is a pilot study, formal hypothesis testing of the study variables will not be performed and multiple testing procedures are not incorporated in the statistical analysis.

## 9.2 Multi-centre Trial Considerations

A maximum of five (5) clinical sites will participate in the study. The maximum enrolment at any one site will be 20 subjects.

This is therefore a multi-centre clinical study with standardization of subject enrolment, data entry and adverse event reporting. All investigational sites will follow the requirements of a common protocol, data collection procedures and forms.

Data will be presented in summary form for all subjects enrolled. Given the intended sample size, formal tests of poolability are expected to have low power and will not prospectively be performed but primary variables will also be presented separately for each center.

## 9.3 Interim Analysis

No formal interim analyses are defined for purposes of early study termination.

## 9.4 Sample Size

As formal hypothesis testing is not a study objective, the sample size is based on precision of estimation.

A sample size of up to 45 subjects enrolled, with at least 30 subjects providing evaluable safety data, gives a standard error for the primary safety variable between 4.5% and 5.4%, which is sufficient for estimation of the safety incidence rate.

## 9.5 Number of Clinical Sites

A maximum of five (5) clinical sites will participate in the study. The maximum enrolment at any one site will be 20 subjects.

## 10 Additional Trial Characteristics

 Cerius Endovascular	Document Number	Rev F	Page 19 of 34
	DNX065-01		
Design History Document	Title		
Confidential & Proprietary	Clinical Investigation Plan, Contour Neurovascular System™		

## 10.1 Measures Taken to Avoid Bias

Several measures have been included in the CIP in avoidance of bias, including the following:

1. The study has been designed to ensure treatment and follow-up of subjects are consistent with current medical practice.
2. The study will be approved by the central Ethics Committees (ECs) prior to initiation and will undergo continuing review by the ECs as the study progresses. Additionally, each clinical site will provide further oversight and approval of the study.
3. All investigators must disclose potential conflicts of interest, including financial interests, to the study sponsor prior to participation in the study.
4. Data from all investigative sites will be monitored throughout the study.
5. An independent Medical Monitor will adjudicate adverse events that may be considered serious and/or device related.
6. Imaging obtained during the procedure and follow-up period will be reviewed by an independent Core Laboratory to verify the status of the Contour implant and the surrounding vasculature.

## 10.2 Special Equipment for Investigation

Apart from the study device, all equipment used in the trial will be maintained and calibrated in accordance with the clinical site institution's policies and procedures and will be reviewed as part of routine monitoring visits.

## 10.3 Procedure for Replacing Withdrawn Subjects

Subjects who withdraw from the study will not be replaced.

## 10.4 Subject Pregnancy

The exclusion criterion specifies that those patients who are pregnant, breastfeeding or planning pregnancy in the next two years be excluded from the study. Should a subject become pregnant after enrolment in the study, the subject will continue to be seen by the investigator at the time points defined in the CIP to ensure proper follow-up of the subject. The subject will be assessed for any new adverse events, undergo a standard neurologic examination, a modified Rankin Scale (mRS) score will be recorded and a NIH Stroke Scale will be recorded if a stroke has occurred. It is expected that the cerebral angiogram required at a specific follow-up visit will not be completed if the subject is pregnant or breastfeeding. Additionally, if a subject is pregnant or breastfeeding, any other imaging specified by the CIP for a specific follow-up visit will only be completed with the concurrence of the subject's obstetrician/pertinent clinician.

## 10.5 Investigational Device(s) and Comparator(s)

The investigational device is the Contour Neurovascular System™. No comparator devices will be used in the study.

## 10.6 Justification for Comparator

This study has no concurrent comparator as this is a pilot study.

## 10.7 Other Devices Used During Study

Several devices are standardly used during endovascular procedures to treat IAs. Other than the investigational implant and implant delivery system, no special devices are required for this study.

	Document Number	Rev F	Page 20 of 34
	DNX065-01		
Design History Document	Title		
Confidential & Proprietary	Clinical Investigation Plan, Contour Neurovascular System™		

## 10.8 Investigational Devices

A single investigational device is expected to be used for each target IA. In some situations, an investigational device might be inserted into the body but removed prior to deployment, in which case another device package could be opened and used.

Device accountability records should be maintained at each study site. The quantity of devices received by the study site, those returned to the sponsor (if applicable), and those devices used at the clinical site will be recorded in the device accountability record. The investigator must explain in writing the reasons for any discrepancy noted in device accountability. Device accountability will be verified during routine monitoring visits at the clinical sites.

## 10.9 Total Expected Trial Duration

Enrolment is expected to be complete in 6 months. The investigation is expected to last at least 5 ½ years, including enrolment.

# 11 Study Management

This study will be run according to ISO 14155:2011, the Declaration of Helsinki, conditions imposed by local ethics committees (ECs), and any applicable regulatory requirements. For this study, the sponsor will have certain direct responsibilities and may delegate other responsibilities to appropriate consultants and/or contract research organizations (CROs). Together, the sponsor and all related participants will ensure that the study is conducted according to the above standards and all applicable regulations. All personnel to participate in the conduct of this clinical trial will be qualified by training, education and/or experience to perform his or her respective tasks.

## 11.1 Investigator Responsibilities

This section highlights responsibilities of the principal investigator (PI) at each site regarding this investigation. The PI, i.e., the main investigator at each study site, is responsible for managing day-to-day aspects of the study. The PI will take steps to ensure compliance with the CIP and associated documents and processes. The PI also protects data integrity and the rights, safety and well-being of clinical study subjects.

### 11.1.1 Disclosure

All investigators must disclose potential conflicts of interest, including financial interests, to the study sponsor, both before and during conduct of the clinical study as well as up to 1 year after the study has completed.

### 11.1.2 Additional Site Team Members

The site may add new members to the investigational team. Training of new personnel will be documented before new personnel participate in the study. New investigators should disclose potential conflicts, as described in **Section 11.1.1**.

 Cerus Endovascular	Document Number	Rev F	Page 21 of 34
	DNX065-01		
Design History Document	Title		
Confidential & Proprietary	Clinical Investigation Plan, Contour Neurovascular System™		

### 11.1.3 Communications with EC

The site Principal Investigator (PI) and the site clinical study team are responsible for communication with site ethics committee. The Sponsor and/or designee is responsible for communication with central ethics committees. The PI will:

- provide the sponsor with copies of any relevant EC communications regarding this CIP
- comply with requirements from the EC regarding the CIP
- obtain written/dated approval/favourable opinion from the site EC, before starting the study or recruiting subjects
- obtain written/dated approval from the site EC before implementing any changes in a CIP amendment
- ensure the timeliness of safety reporting to the site EC
- promptly report deviations from the CIP to the EC that affect the rights, safety or well-being of the subject or the scientific integrity of the CIP
- keep all EC communications in its study file

### 11.1.4 Informed Consent

The PI is responsible for the informed consent (IC) process in this CIP. The PI will ensure that:

- the IC used for the consent process is the most current IC, has been approved by the EC and is consistent with any requirements imposed by the EC
- the IC process occurs consistent with ISO 14155, and importantly, prior to any procedure specific to the clinical investigation is applied to the subject.
- a copy of the signed/dated IC form is kept in the subject's records, and
- either he/she or an authorized designee conducts the consent process consistent with ISO 14155

### 11.1.5 Subject Identification Log

The PI or designee will maintain a log of all subjects enrolled in the study. The log links study identification (ID) numbers to identifying patient information (name, contact information). The log will be housed securely.

### 11.1.6 Compliance with CIP

The PI is responsible for ensuring that his/her site complies with the CIP. The PI will:

- maintain oversight of the study at the clinical site
- sign an investigator agreement form
- conduct the investigation in compliance with this CIP, applicable sections of ISO 14155, and requirements of the EC to ensure the safety and well-being of study subjects
- create, maintain and make available source documents for study subjects
- not implement any change to the CIP without prior approval from the sponsor, local EC, and (if required) regulatory bodies
- document all deviations from the CIP
- ensure proper use and accountability of investigational devices
- ensure that the site has adequate staff and capabilities
- ensure that site equipment used in the study is maintained and calibrated

 The sponsor may also document deviations from the CIP.

 Cerius Endovascular	Document Number DNX065-01	Rev F	Page 22 of 34
Design History Document	Title		
Confidential & Proprietary	Clinical Investigation Plan, Contour Neurovascular System™		

- ensure the accuracy, completeness and timeliness of study data in CRFs and reports
- allow and support sponsor monitoring and auditing activities
- be available to monitors and the sponsor to address questions during study visits
- be available and support regulatory authorities during audits
- respond in a timely manner to sponsor inquiries
- make reasonable efforts to prevent early withdrawal
- make reasonable efforts to ascertain the reason for early withdrawal

### 11.1.7 Subject Records

The Investigator will maintain original source documents from which study-related data are derived, which include, but are not limited to:

- Clinic progress notes recording subject's medical history and medications
- Medical charts with operative reports and condition of subject upon discharge
- Medical records regarding AEs, including treatment and clinical outcome
- Results of diagnostic examinations
- Results of subject questionnaires
- Imaging (such as x-rays, angiograms, CTs, MRIs) as well as any existing reading or interpretation of diagnostic imaging
- Notes of phone calls and/or correspondence indicating investigational site's attempts to follow study subjects at the required follow-up visits until subject's participation in the study is complete or terminated
- Records relating to patient death (e.g., death certificate, autopsy report/terminal medical records)
- Printouts of source data generated by technical equipment (e.g., x-rays, MRIs) must be filed with the patient's records.

### 11.1.8 Subject Accountability

The PI will make reasonable efforts to account for all study subjects, especially those who withdrew. If withdrawal is due to problems with study device safety or performance, the PI will obtain the subject's permission to follow his/her status/condition outside the clinical investigation, if possible.

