## 7.10 Early Withdrawal

Reasons for subject withdrawal prior to study completion will be documented on the CRF. Valid reasons for early study withdrawal include:

- Death
- Adverse event or other medical condition that prevents study participation
- Withdrawal of voluntary consent
- Loss to follow-up

 Cerus Endovascular	Document Number	Rev F	Page 15 of 34
	DNX065-01		
Design History Document	Title		
Confidential & Proprietary	Clinical Investigation Plan, Contour Neurovascular System™		

- Study is terminated

At least three documented attempts will be made to contact any subject who is lost to follow-up. If the study is terminated for any reason, the governing Ethics Committee will be notified.

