## 7.11 Variables

### 7.11.1 Primary Variables

The primary variables are safety as this is a pilot study.

The safety variables to be collected and reported are the occurrence and frequency of AEs, ADEs, SAEs, SADEs and USADEs.

Specific AEs associated with this procedure that shall be evaluated include but are not limited to: blood vessel perforation or rupture, unintended thrombosis, adverse tissue reaction, infection, and hematoma formation, and major ipsilateral stroke/ SAH or death due to neurologic cause within 6 months after treatment.

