### 11.2.12 Safety Reporting

The sponsor is responsible for ongoing safety evaluation in this CIP. Sponsor activities regarding safety include:

- ensuring the independent Medical Monitor reviews all adverse events to ensure they are reported accurately and in sufficient detail,
- classification of all AEs
- review of all AEs reported in the study
- confirm site's classification of AEs in terms of severity and relatedness to the study device
- review of device deficiencies and malfunctions, including determination and documentation of whether deficiencies/malfunctions could have led to an SAE
- ensuring the reporting of all SAEs and device deficiencies/malfunctions that could have led to an SAE to the EC and, if required, regulatory authorities in a timely fashion
- informing all site PIs in writing of all SAEs at all sites in a timely fashion
- ensuring that the EC and the regulatory authorities are informed of significant new information about the clinical investigation
- updating the risk analysis and assessment of corrective or preventive actions potentially required as a result of new information obtained in the investigation

The sponsor will evaluate all serious adverse events. The sponsor will investigate each SAE to determine whether the event represents an unanticipated serious adverse device effect (USADE). The sponsor will report any event to regulatory authorities, investigators and reviewing ECs as necessary. If an investigation shows that a USADE presents an unreasonable risk to subjects, the sponsor will terminate all investigations or parts of investigations presenting that risk as soon as possible. The sponsor will only resume a terminated investigation after corrective actions have taken place, site investigators are informed and ECs have been notified and given approval to resume the study.

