#### 11.2.14 Suspension or Termination of Study

The sponsor may temporarily suspend or terminate the study at any time at one or more sites for the following reasons:

- Suspicion of risk to patients, including occurrence of high rate of known AEs or unexpectedly high rate of unexpected AEs
- Poor site compliance with this CIP
- Inadequate site enrolment
- Obtaining new scientific knowledge that shows that the study is no longer valid or necessary
- Persistent non-compliance with EC or regulatory requirements
- Persistent failure to comply with obligations arising from the clinical trial agreement • Other business reasons (e.g., insolvencies or business entity liquidation)

The sponsor will document reasons for study suspension and notify relevant site PIs and the coordinating investigator. The sponsor will ensure that the EC and regulatory authorities (if required) are notified in a timely manner. If suspension occurred because of a safety issue, all site PIs will be notified. When terminating the study, the sponsor and investigator will assure that adequate consideration is given to the protection of the subjects' interests.

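### Harm that occurs after withdrawal for an adverse event or device problem has no stated route into the primary safety counts, although the subject still carries the implant and stays in the denominator

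*Combined protocol and SAP*

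**What the plan says.** Section 7.10 introduces its list with "Valid reasons for early study withdrawal include". Beside death, withdrawn consent and loss to follow-up, the list contains "Adverse event or other medical condition that prevents study participation" and "Study is terminated". The section asks for the reason to be recorded. Its three contact attempts apply to subjects lost to follow-up.

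Section 11.1.8 asks the investigator for reasonable efforts to account for all subjects, particularly those who withdrew. Where the withdrawal is due to device safety or performance, the investigator is to obtain the subject's "permission to follow his/her status/condition outside the clinical investigation, if possible".

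Section 7.11.1 makes safety primary: AEs, ADEs, SAEs, SADEs and USADEs, with no time limit, plus named events that include major ipsilateral stroke/SAH or "death due to neurologic cause within 6 months after treatment". Section 9.1 says that the primary analysis "will include all available data for all enrolled subjects" and that adverse events are analysed primarily by subject, with event counts also tabulated. It has no rule for missing data, censoring or person-time. Section 10.3 does not replace withdrawn subjects.

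**The concern.** Safety is the primary objective, and visits are planned to five years (section 7.9). The implant is detached and left in the aneurysm (section 7.7.4). Section 6.1 lists recanalization, and migration leading to haemorrhage or ischemic stroke, without confining either to the procedure. A subject withdrawn because of an adverse event or a device problem remains exposed to these risks.

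Follow-up then ends because the subject has had a problem, so the loss may be related to the outcome. That these subjects are at higher risk afterwards is a reasonable inference, not a statement in the CIP. With an all-enrolled denominator, a later event that is not captured counts as no event.

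The gap reaches oversight as well as tables. The Medical Monitor reviews reported adverse events (section 8.2), and the sponsor updates the risk analysis from information obtained in the investigation (section 11.2.12).

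**Working it through.** **1. The plan's own precision figure.** Section 9.4 gives a standard error of 4.5% to 5.4% for up to 45 enrolled and at least 30 evaluable subjects, without stating an event rate. Assume p = 10% in SE = √(p(1−p)/n):

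- n = 45: √(0.10 × 0.90/45) = 4.47%
- n = 30: √(0.10 × 0.90/30) = 5.48% (n = 31 gives 5.39%)

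The range is reproduced closely, with 4.5% belonging to 45 subjects and 5.4% to about 30. It describes sampling error only.

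**2. Which categories can lose a subject.** The primary analysis counts subjects, so only a category that the subject has not yet reached can change. As an illustration, suppose a device-related event at week 8, withdrawal, and a major ipsilateral stroke at month 4 that meets the SAE definition:

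| Category | Week-8 event not serious | Week-8 event serious |
|---|---|---|
| AE, ADE | already counted | already counted |
| SAE | missed | already counted |
| SADE (if the stroke is device-related) | missed | already counted |
| Six-month stroke/SAH/neurologic-death item | missed | missed, unless the week-8 event already met it |

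The six-month item is affected only by withdrawal before six months. The general categories are open to loss over the whole five years. The supplementary event counts would lose every later event.

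**3. Size per subject.** Section 9.1 refers to all enrolled subjects, so the denominator at full enrolment is 45.

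- Shift from one missed subject: 1/45 = 2.2 percentage points
- Relative to the matching standard error: 2.22/4.5 = 49%

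**4. Range.** The CIP gives no withdrawal rate and no event rate after withdrawal. Assuming that one to three subjects have a missed event in a category new to them, the understatement is 1/45 = 2.2, 2/45 = 4.4 or 3/45 = 6.7 points. If 4 of 45 had been counted in that category (8.9%, also an assumption), complete follow-up would give 5/45 = 11.1%, 6/45 = 13.3% or 7/45 = 15.6%.

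**5. Does another section close the gap?** Section 8 requires all adverse events on a CRF, but says nothing about events after participation ends. Section 11.1.7 keeps notes of follow-up attempts only until participation is complete or terminated. Close-out (section 11.2.10) documents the status of events already ongoing, not new ones. By contrast, section 10.4 keeps a pregnant subject in the study for adverse events, neurologic examination and mRS when angiography is expected to be omitted. The CIP thus already separates imaging from safety follow-up in one case. It does not do so for a subject withdrawn for an adverse event.

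**The case against.** The strongest reply is that the CIP is silent rather than restrictive. Section 9.1 refers to all available data, with no limit to CRF or on-study data. Section 11.1.8 asks for reasonable efforts to account for withdrawn subjects, and section 11.1.6 for reasonable efforts to prevent withdrawal and to learn its cause. Section 7.5 says that implanted subjects are followed for the duration of the study. Section 7.10 covers only adverse events that prevent participation. The request for permission in section 11.1.8 also fits a subject who has chosen to leave.

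Much of this stands. A reader might infer that outside information is barred from the analysis; no sentence says so. What remains is that no rule collects, adjudicates or counts it, so sites may differ and the default is omission.

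Other stronger readings also fail:

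- **Every later event lowers the reported proportion.** Subject counts limit the loss to new categories.
- **One missed event is worth 1/30 = 3.3 points.** That uses the evaluable minimum, which conflicts with keeping the subject in the all-enrolled denominator.
- **The bias always favours the device.** This fails if withdrawn subjects are dropped as non-evaluable. With 4 counted events, dropping one subject gives 4/44 = 9.1%. That is below 5/45 = 11.1% if the subject had a later event, but above 4/45 = 8.9% if not.
- **A safety termination biases the counts.** Section 11.2.12 says of a USADE that presents an unreasonable risk that "the sponsor will terminate all investigations or parts of investigations presenting that risk as soon as possible". It does not say that follow-up of implanted subjects stops. Termination of the whole study would also shorten follow-up for everyone rather than for a selected group. Section 11.2.14 asks that "adequate consideration is given to the protection" of subjects' interests, which leaves data collection open. This is an ambiguity to reconcile, not a demonstrated bias.

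**Conclusion.** The point holds as a design weakness that is cheap to correct. Followed as written, sections 7.10 and 11.1.8 allow later harm to go unrecorded in implanted subjects who leave because of an adverse event or device problem, and nothing returns that harm to the primary counts. The tendency is to understate categories the subject had not yet reached.

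The size is 2.2 points per affected subject, about half the 4.5% standard error. This assumes 45 enrolled, an all-enrolled denominator, an implant in place and a later event in a new category. The total cannot be estimated from the CIP, and the one-to-three range is only illustrative. As a descriptive pilot with no hypothesis test, the study has no test decision at stake; what is affected is how completely the safety profile is reported.

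**What to change.** In sections 7.10 and 11.1.8, separate stopping study visits or imaging from ending safety data collection. Unless the subject withdraws consent, dies or is lost to follow-up, continue to record adverse events, vital status and mRS in the study, by telephone or from records, at the Table 3 time points. Enter them in the CRF, send the adverse events to the Medical Monitor and count them in the primary variables. Keep follow-up outside the investigation for withdrawn consent.

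In section 9.1, add a report of how many subjects were withdrawn for adverse events or device problems, with their follow-up time.

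For suspension or termination, reconcile sections 7.10, 11.2.12 and 11.2.14 on whether safety data from implanted subjects continue to be collected.

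The cost is CIP and consent wording and a few remote contacts. The reported event rate may come out slightly higher.
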